#### *Training and ongoing supervision*

Therapists will be qualified Psychological Well-being Practitioners (PWPs), employed within an NHS trust. Prior to delivering the intervention, therapists will receive training over 2 to 3 days. This will cover training in ACT, the context of AML, and the specific treatment package. PWP therapists will receive regular group supervision with registered practitioner psychologists.

#### *Referral to specialist services*

If, at any stage, it becomes clear the participant requires more intensive psychological support (i.e. suicide risk) they will be referred to local clinical psychology services.

**Physical activity:** A measurable dose of individualised multi-modality physical activity prescribed and supervised remotely by a specialist Clinical Exercise Physiologist in hospital or at home, to address general fitness, functional strength and fatigue [35], in accordance with American College Sports Medicine Guidelines [36]. To counter fatigue, focus will be on purposeful, prescribed and structured exercise [37], however, general physical activity recommendations will also be promoted. To accommodate transient changes in participants' wellbeing, the programme will adopt the principles of autoregulation whereby exercise is

progressed/regressed based on self-perceived daily variations in health, performance capability, recovery, and treatment [38].

The online, supervised, programme will consist of up to 30 minutes exercise two to three times per week. Participants will be encouraged to attend two live on-line sessions every week in discrete groups (max 6) or individually as required. Due to the complexity of health needs only Can Rehab professionals with suitable and recent experience in managing patients with complex conditions will supervise the intervention. Additionally, participants will be able to access online, pre-recorded sessions. A link will be provided to participants weekly for a specific session prescribed individually by the Clinical Exercise Physiologist.

*Physical activity safety:*

All participants will be assessed for any additional underlying health conditions or complications related to AML. All supervised sessions will be led by staff experienced in remote on-line assessment, prescription, and delivery of exercise for multi-morbid clinical populations. Pre-exercise session clinical screening will be completed. Staff will also monitor for adverse events during the sessions.

All participants will be advised to have another person nearby for the exercise sessions. When participants are joining from home, emergency contact information will be collected. In the event of an emergency, the practitioner will alert the designated 'co-pilot' for the session who will be able to communicate directly with the participant in question (via the live call or telephone) outside of the group and alert the emergency services if required.

**Nutritional support:** PPCP nutritional assessment will be delivered by a qualified dietitian as part of the central PROPEL specialist team utilising the dietetic care process [39] and informed by the pre-screening clinical data provided by the local HCP (see above for details). Intervention constituents will aim to facilitate improvements in cancer related fatigue via optimising dietary quality [40] and macronutrient provision tailored to individual requirements [41]. Energy and protein requirements will be based on ESPEN guidelines [42] and clinical expertise in AML at 25-30kcal/kg/d (utilising a Physical Activity Level (PAL) depending clinical appropriateness) and 1.2-1.5g protein/d. Recommendations and resources will be provided on timing of protein intake in relation to exercise in order to optimise muscle recovery [43]. Where appropriate patients will have access to nutritional supplements at site to meet energy or protein deficits in their intake. The PROPEL dietitian will work with local HCPs to support delivery (including supplement prescribing), in order to ensure parity in treatment access for intervention and control patients, accounted for in site agreements.

A rolling programme of group virtual support sessions, alongside online bite-sized nutrition education videos will be available to participants. The content will include principles of the PROPEL diet, known barriers to intake in this group informed by PPI and HCP experiences, for example, nausea/taste changes, altered bowels, protein and energy intake. Content will provide practical advice for managing these barriers and re-emphasise some of the

psychological skills from the emotional well-being modules that may be helpful (e.g., unhooking). Use of behaviour change techniques such as goal setting and self-monitoring will also be encouraged. A virtual 1:1 dietetic appointment will be given each cycle to those requiring nutritional supplements. Additional 1:1 sessions may be offered on individual need where there is an identified concern raised, e.g. during their MDT, or by the local intervention HCP or patient during their weekly catch-up sessions. All prehab care plans will be updated as required.

*Referral to specialist services:*

Local PROPEL-trained HCPs will be supported to facilitate transfer to hospital based dietetic services where there is a clinical indication for enteral feeding, parenteral nutrition, specialist nutritional supplements (i.e. renal products, elemental diet) or the patient has refeeding syndrome at any stage in the trial. If a clinical risk then abates, nutrition advice can continue for subsequent cycles.

**Local behavioural support:** Local trained (unblinded) HCPs, where possible, will contact the participant (either face to face, by phone or video call) on a weekly basis for a brief check-in (15-30 minutes) to discuss any challenges and offer opportunities for reflections on their behaviour in relation to their goals and values. The HCP will support them to keep going by providing social support, the use of problem solving and action planning, and encouraging practice of their 4 psychological skills. The remote specialist team will act as an expert advice line to the local upskilled HCP.

Attendance to all sessions will be monitored, and participants or their local HCP will be contacted by a PROPEL practitioner in order to ascertain the participants welfare should any concerns arise due to non-attendance.

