### 2.2.2 Secondary Outcomes:

- Emotional wellbeing: the Warwick-Edinburgh Mental Wellbeing Scale (WEMWBS) assesses participant's mental wellbeing and consists of 14 items, scored on a 5-point Likert scale score, giving an overall score [12].
- Anxiety and Depression: Patient Health Questionnaire 9-item (PHQ9) measures severity of depression and response to treatment. General Anxiety Disorder 7-item (GAD7) assesses the likelihood of the presence of the four most common clinical anxiety disorders [13, 14].
- Health-related quality of life:
  - FACIT F incorporates the 27 item FACT-G (Functional Assessment of Cancer Therapy – General) and measures four domains of health-related quality of life: physical, social, emotional and functional well-being.
  - EQ-5D-5L measures health status in 5 dimensions plus a visual analogue scale of self-rated health status [15].
- Physical function:
  - Performance Status: the Karnofsky Performance Scale Index allows patients to be classified as to their functional impairment, used in (p)rehabilitation [16].
  - The 6-minute walk test [17].
  - Hand grip strength [18].
- Incidence of sarcopenia: SARC-F [19]; calf circumference [20].
- Incidence of malnutrition: Utilising Malnutrition Universal Screening Tool (MUST) [21] and its determinants; % weight change, Body Mass Index (BMI), energy and protein intake (food diaries via myfood24) [22].
- Completion of consolidation treatment plan (chemotherapy +/- HSCT)
- Number of onward referrals to local services for 'specialist' therapies.
- Overall and relapse-free survival.
- Readmissions to hospital, ICU admission, number of transfusions, complications of HSCT, adverse events and serious adverse events.
- Costs, cost-effectiveness and utility: costs, health resource use and EQ-5D-5L.
- Process Evaluation: fidelity to intervention delivery and dose of intervention received for each component.
- Mechanisms of Action:
  - Psychological flexibility – is the mechanism of action for ACT, and the model within which all intervention methods are delivered. This will be measured with a shortened version (8-items) of the CompACT questionnaires [23]
  - Motivation – measured using 1-item from the COMB-Q adapted for each component (3-items total) [24].

All questionnaires being used for the patient reported outcomes have been previously validated or have been adapted from validated questionnaires to fit this specific context and patient group.

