#### **4.8 Fidelity**

Competency of those delivering the interventions will be assured through training which will include assessment of delivery at an early session, feedback and identification of additional training needed. These assessments will be included in the practitioner manual.

We will assess fidelity to each of the intervention components by those delivering them and how well patients are able to adhere to their programmes. Adherence will be assessed to calculate a measure of 'dose' of the intervention received and comprise of assessment of the proportion of prescribed sessions attended and, as appropriate, through assessment tools designed by the study team. The tools will be completed by those delivering the interventions at sessions. The assessment information will provide information about the amount of intervention participants were able to receive compared with published guideline recommendations, where available, or with a study standardised clinical assessment of how much of their prescribed dose they received. Delivery team practitioners will encourage patients to log their activities and bring these logbooks to sessions to inform the practitioners' assessment of intervention received. More information about the proposed content of these assessment is given below by intervention component. Participants ability to do their prescribed activities may fluctuate with how well they feel during their treatment cycles, so, where possible reasons for non-attendance at sessions or completion of activities will be noted.

An overall assessment of delivery team adherence to theoretical basis (behaviour change techniques and ACT) of the intervention package will be conducted. Thirty recordings, selected at random across the diet, exercise, and emotional wellbeing sessions will be listened to by the central team health psychologist and assessed for inclusion of pre-specified behaviour change techniques and broad adherence to ACT principles (e.g., using ACT-FM Stance items (4 prescribed and 3 proscribed) [44].

As this is a new way of delivering interventions together in a package, where possible, we will conduct analyses to see whether there were differences in key outcomes according to 'dose' received.

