
Nutrition: PROPEL dietitian in central specialist hub (in collaboration with local PROPEL trained HCPs)
	
Delivery fidelity:
 
 
• Proportion of planned nutrition sessions delivered and reasons for non-delivery.
 
• No. of views for the online bite-size education videos
 
• Proportion of patients being escalated to local care due to complex needs.
 
• A random sample of recorded nutrition group sessions will be independently (where possible) assessed using a trial specific checklist to assess delivery of fatigue improving interventions.
 
	
Proportion of nutrition sessions attended plus assessment of requirement for additional queries made by patients, carers and local PROPEL trained HCPs outside the scheduled sessions (i.e., numbers of queries)
 
The practitioner will use the following sources of information to make an assessment of “dose” received using a trial specific checklist/tool.
 
Logbook: participants will be asked to log if they were able to adhere to their recommended nutrition treatment plan.
 
Food diary: information from food diaries will determine patient capacity to adhere to nutritional treatment plans in the following ways:

		
 
• Nutritional deficits between reported energy and protein intakes (calculated via myfood24 from 3-day food diaries) will be compared to recommended targets.
 
• Number of recommended nutritional supplements versus those taken (also available from patient prescriptions).
 

Wellbeing: Central research team/PROPEL trained psychologists
	
Practitioner treatment fidelity will be assessed through independent (where possible) rating of a random sample of 30 tapes (of sessions 2 -5) using the ACT-Fidelity Measure (ACT-FM) [44]
	
Proportion of offered sessions received and reasons for non-attendance.

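### The protein requirement is printed as 1.2-1.5 g per day, beside an energy requirement per kg per day; a per-kg basis is almost certainly missing.

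*Protocol*

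**What the plan says.** Section 4.6.2 (Nutritional support) bases energy and protein requirements on a cited guideline and "clinical expertise in AML at 25-30kcal/kg/d (utilising a Physical Activity Level (PAL) depending clinical appropriateness) and 1.2-1.5g protein/d". One sentence holds both figures. The energy figure carries a per-kg term and the protein figure does not.

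The target has stated or natural uses elsewhere:

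- **Supplements (section 4.6.2):** "Where appropriate patients will have access to nutritional supplements at site to meet energy or protein deficits in their intake".
- **Dietetic contact (section 4.6.2):** "A virtual 1:1 dietetic appointment will be given each cycle to those requiring nutritional supplements".
- **Nutrition dose (section 4.8, Table 2):** "Nutritional deficits between reported energy and protein intakes (calculated via myfood24 from 3-day food diaries) will be compared to recommended targets".
- **Dose analysis (section 5, Data analysis):** dose is calculated for each component from the Table 2 data, and its association with key outcomes is explored.

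No other section gives a numerical protein target or corrects this one. The pre-MDT screening in section 4.6.2 records weight in kg, so a per-kg target could be calculated.

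**The concern.** An absolute requirement of 1.2-1.5 g of protein a day is not a nutritional target, because almost any food intake exceeds it. It also conflicts with the aim, stated in the same paragraph, of fitting macronutrients to the individual: a flat figure takes no account of body size, while the energy figure beside it does.

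If the printed figure were used, only a near-zero intake would count as a protein deficit. The protein part of the supplement decision would then have no discriminating value. The same holds for the protein part of the Table 2 comparison, if its targets are those of section 4.6.2. A dietitian would probably notice. Someone programming the dose tool, or a service reproducing the intervention from the protocol, might not.

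**Working it through.** The protocol gives no derivation of the protein figure, so there is no calculation of its own to reproduce. The check is one of units and plausibility, using the protocol's own energy target.

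**Inputs from section 4.6.2:** energy 25-30 kcal/kg/d; protein as printed 1.2-1.5 g/d.

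**Assumptions not in the protocol:** 4 kcal per g of protein; body weight 70 kg, with a range of 50-100 kg.

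**Formula:** protein share of energy = 4 × protein (g/d) ÷ [energy (kcal/kg/d) × weight (kg)].

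**As printed.** Protein energy is 4 × 1.2 = 4.8 to 4 × 1.5 = 6 kcal/d. At 70 kg the energy target is 25 × 70 = 1750 to 30 × 70 = 2100 kcal/d. The share runs from 4.8/2100 = 0.23% to 6/1750 = 0.34%.

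**Read per kg.** Protein energy is 4.8-6 kcal/kg/d and weight cancels. Pairing like ends of the two ranges gives 4.8/25 = 19.2% and 6/30 = 20.0%. Pairing opposite ends gives 4.8/30 = 16.0% and 6/25 = 24.0%.

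| Weight (kg) | Energy target (kcal/d) | Share of energy as printed | Protein if per kg (g/d) | Share of energy if per kg |
|---|---|---|---|---|
| 50 | 1250-1500 | 0.32-0.48% | 60-75 | 16-24% |
| 70 | 1750-2100 | 0.23-0.34% | 84-105 | 16-24% |
| 100 | 2500-3000 | 0.16-0.24% | 120-150 | 16-24% |

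The printed figure is smaller than the per-kg reading by a factor equal to body weight in kg: 84/1.2 = 70 at 70 kg, and 50 to 100 over the range shown.

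**Consequence for classifying a deficit.** At 70 kg, any intake from 1.5 g up to 84 g a day is a deficit on the per-kg reading and no deficit on the printed one.

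**The case against.** The strongest reply is that the slip corrects itself. The energy unit stands beside it, the guideline is named, and an error of 50-100 fold is too large to mislead a qualified dietitian, who makes the assessment. Supplements are offered where appropriate, which is clinical judgement and not a numerical threshold, and extra 1:1 sessions can be given on individual need. Table 2 does not say that its targets are the section 4.6.2 figures. Section 4.8 allows dose to be compared with "published guideline recommendations, where available, or with a study standardised clinical assessment of how much of their prescribed dose they received". Energy deficit, attendance, logbook and supplement inputs to the dose measure still work. Finally, loss of the per-kg term when the text was read from the PDF cannot be fully excluded.

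Most of this stands as a limit on the consequence. The link to Table 2 is the natural reading but is inferred, and the protocol does not show whether the practitioner manual or dose tool carries the same figure. Loss in text extraction is unlikely, because the energy unit survives intact in the same sentence and the protein phrase reads without a gap.

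None of it makes the printed figure right. This is current text specifying the intervention, it is the only protein figure given, and it is not a detail that would be left to a statistical analysis plan.

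**Conclusion.** The figure is wrong as written, and the severity is minor. The missing per-kg basis is inferred from the parallel energy unit and from the arithmetic: about 0.2-0.3% of energy as printed at 70 kg, against 16-24% per kg at any weight. The inference rests on 4 kcal per g and, for the printed reading, weights of 50-100 kg; no plausible weight rescues that reading. The cited guideline was not available, so the exact corrected value needs confirmation.

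The reach is limited to the protein part of the supplement decision and, probably, one of several inputs to the nutrition dose measure. The secondary outcome in section 2.2.2 is protein intake, not deficit, so it is unaffected. The primary outcome, the intention-to-treat comparison and the sample size do not use the figure. Practical harm is improbable and cannot be shown from the protocol.

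**What to change.** - Change the unit in section 4.6.2 to 1.2-1.5 g protein/kg/d, after the trial dietitians confirm it against the cited guideline.
- Check that the practitioner manual, the Table 2 comparator and the nutrition dose tool use the same basis.
- If any protein deficit has been calculated against the printed figure, recompute it from the stored food diaries. Nothing in the protocol shows that this has happened.

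The cost is a one-unit wording change in the next amendment and a short document check. No new data are needed and participants have no extra burden.

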## **4.7 Resources and support materials:**

### **4.7.1 Local practitioner manual**

A practitioner manual will guide local practitioners through each component of the intervention and emphasise the ACT principles and behavioural strategies that will guide all practitioners throughout their delivery of the PPCP. The manual will reflect information provided during training and also include general information about the trial, key components of GCP, and contact details of the study team.

### **4.7.2 Participant manual**

A participant manual will be a resource detailing, in a patient-friendly fashion, all information relating to the trial. Both the BPUC and PPCP manual will include:

- 1) general information about the trial
- 2) background information about AML
- 3) contact details and links to online resources.

The PPCP manual will additionally include

- 1) Information on emotional well-being, physical activity, and nutrition to support the remote sessions
- 2) Top tips for common problems
- 3) A logbook to support self-monitoring
- 4) Additional behaviour change strategies

#### **4.8 Fidelity**

Competency of those delivering the interventions will be assured through training which will include assessment of delivery at an early session, feedback and identification of additional training needed. These assessments will be included in the practitioner manual.

We will assess fidelity to each of the intervention components by those delivering them and how well patients are able to adhere to their programmes. Adherence will be assessed to calculate a measure of 'dose' of the intervention received and comprise of assessment of the proportion of prescribed sessions attended and, as appropriate, through assessment tools designed by the study team. The tools will be completed by those delivering the interventions at sessions. The assessment information will provide information about the amount of intervention participants were able to receive compared with published guideline recommendations, where available, or with a study standardised clinical assessment of how much of their prescribed dose they received. Delivery team practitioners will encourage patients to log their activities and bring these logbooks to sessions to inform the practitioners' assessment of intervention received. More information about the proposed content of these assessment is given below by intervention component. Participants ability to do their prescribed activities may fluctuate with how well they feel during their treatment cycles, so, where possible reasons for non-attendance at sessions or completion of activities will be noted.

An overall assessment of delivery team adherence to theoretical basis (behaviour change techniques and ACT) of the intervention package will be conducted. Thirty recordings, selected at random across the diet, exercise, and emotional wellbeing sessions will be listened to by the central team health psychologist and assessed for inclusion of pre-specified behaviour change techniques and broad adherence to ACT principles (e.g., using ACT-FM Stance items (4 prescribed and 3 proscribed) [44].

As this is a new way of delivering interventions together in a package, where possible, we will conduct analyses to see whether there were differences in key outcomes according to 'dose' received.

**Table 2- Fidelity**

Component and who delivers it	Delivery Fidelity	Patient adherence and assessments of “dose” of interventions received

Local behavioural support: Local PROPEL trained Health Care Professional (HCP) at site
	
Number of weekly check ins offered to each patient, detailing any with reasons that this was not offered.
 
Health psychologist assessment of 30 recordings of randomly selected sessions, using a trial designed checklist of fidelity to the protocol.
	
Proportion of offered sessions received and reasons for non-attendance.
 
The local HCP delivering the behavioural support will use the patient’s logbook to assess what the participant was able to complete each week (including any BCTs used where relevant).

Exercise: Centralised Clinical Exercise Physiologist team
	
Proportion of planned sessions delivered and reasons for non-delivery.
 
A randomly selected sample of 30 recordings of sessions will be assessed using a pre-specified checklist by an independent (where possible) clinical exercise psychologist.
	
Due to the changeable nature of how participants may feel in response to treatment, the aim of the exercise component assessment will be to compare dose received with existing guidelines recommendations for exercise in other similar cancer populations.
 
Live sessions: we will calculate dose by recording frequency, intensity, time, and type of exercise for every participant at every live session. This will be documented by the practitioner after each session.
 
Pre-recorded/on-demand sessions: participants will record in their logbook which sessions (if any) they complete each week. This will also be recorded by the practitioner.


Nutrition: PROPEL dietitian in central specialist hub (in collaboration with local PROPEL trained HCPs)
	
Delivery fidelity:
 
 
• Proportion of planned nutrition sessions delivered and reasons for non-delivery.
 
• No. of views for the online bite-size education videos
 
• Proportion of patients being escalated to local care due to complex needs.
 
• A random sample of recorded nutrition group sessions will be independently (where possible) assessed using a trial specific checklist to assess delivery of fatigue improving interventions.
 
	
Proportion of nutrition sessions attended plus assessment of requirement for additional queries made by patients, carers and local PROPEL trained HCPs outside the scheduled sessions (i.e., numbers of queries)
 
The practitioner will use the following sources of information to make an assessment of “dose” received using a trial specific checklist/tool.
 
Logbook: participants will be asked to log if they were able to adhere to their recommended nutrition treatment plan.
 
Food diary: information from food diaries will determine patient capacity to adhere to nutritional treatment plans in the following ways:

		
 
• Nutritional deficits between reported energy and protein intakes (calculated via myfood24 from 3-day food diaries) will be compared to recommended targets.
 
• Number of recommended nutritional supplements versus those taken (also available from patient prescriptions).
 

Wellbeing: Central research team/PROPEL trained psychologists
	
Practitioner treatment fidelity will be assessed through independent (where possible) rating of a random sample of 30 tapes (of sessions 2 -5) using the ACT-Fidelity Measure (ACT-FM) [44]
	
Proportion of offered sessions received and reasons for non-attendance.

